4.7.1.4 Reporting of serious adverse events

Investigators and other centre personnel must inform appropriate AstraZeneca representatives via the web based data capture (WBDC) system of any SAE that occurs in the course of the study within 1 calendar day (ie, immediately but no later than the end of the next business day) of when he or she becomes aware of it.

Follow-up information on SAEs must also be reported by the Investigator within the same time frames.

If follow-up indicates a change in the SAE serious criteria to fatal or life-threatening, this information needs to be available in the WBDC system within 1 calendar day.

If a non-serious AE becomes serious, this and other relevant follow-up information must also be provided to AstraZeneca within 1 calendar day as described above.

The AstraZeneca representative will work with the Investigator to compile all the necessary information and ensure that AstraZeneca receives a report by day 1 for **all** SAEs. The AstraZeneca representative will notify the appropriate Bristol-Myers Squibb Pharmacovigilance contact to ensure regulatory compliance.

All SAEs have to be reported, whether or not considered causally related to the investigational product or to the study procedure(s). All SAEs will be recorded and reported to AstraZeneca in the eCRF as described in Section 4.7.1.2. AstraZeneca or the Investigator is responsible for informing the Ethics Committees of the SAE as per local requirements. Reporting of SAEs to Regulatory Authorities is the responsibility of Bristol-Myers Squibb.

For studies in countries implementing the European Union (EU) Clinical Trials Directive, safety updates/reports to Ethic Committees and Principal Investigators will be taken care of by AstraZeneca, see Section 8.1.

SAE handling using WBDC

SAE information will be entered and submitted into the WBDC system on the relevant eCRF modules. An automated e-mail alert will be sent to the designated AstraZeneca representative who will work with the Investigator to ensure that all the necessary information is available in the system within the required time frames, but taking advantage of the time allocated in those timelines. AstraZeneca representative will send a completed SAE report to the appropriate Bristol-Myers Squibb Pharmacovigilance representative via fax or e-mail.

If the system is unavailable, the Investigator should fax a paper back-up SAE report to the AstraZeneca representative immediately, recognising that the same reporting time frames still apply. The Investigator is responsible for completing the eCRF as soon as the system becomes available again.

4.7.2 Laboratory safety measurements and variables

4.7.2.1 Methods of assessment

Blood and urine specimens will be collected for laboratory analyses. The date and time of sampling will be recorded on the laboratory requisition form. The samples will be processed by a central laboratory and results will be reported back to the clinic within 72 hours.

Due to the fasting laboratory assessments, all patients will visit the clinic on a fasting stomach in the morning, before 1100. The patients will be instructed not to have ingested any food or beverages 8 hours before visiting the clinic (however, drinking water is allowed). Also, the patients will be instructed to not take the investigational product and metformin in the morning before visiting the clinic. Allowed medications can be taken with water only.

All samples should be taken by adequately trained study personnel, and performed and handled in accordance with given instructions in the laboratory manual. Up to date reference ranges will be provided during the study and laboratory results will be compared to the laboratory standard normal ranges and flagged if they are outside the normal range. The Investigator should make an assessment of the available results with regard to clinically significant abnormalities. The laboratory reports should be signed and retained at centre as source data for laboratory variables.

For information on how AEs based on laboratory tests should be recorded and reported, see Section 4.7.1.2.

The complete list of safety laboratory tests is displayed in Table 6 and Table 7 below. The laboratory tests are conducted following the assessment schedule outlined in Section 4.7.2.1.

Table 6 Safety laboratory variables Period A, B, C

Visit number	1	2	3	4	5	6	7	8	9	10	11	12	13
Study week	-21 - 17 days	-2 w	0 w	3 w	6 w	9 w	12 w	15 w	18 w	24 w	30 w	39 w	52 w
Haematology													
Haemoglobin	X		X		X		X		X	X	X	X	X
Haematocrit	X		X		X		X		X	X	X	X	X
Red blood cell count	X		X		X		X		X	X	X	X	X
White blood cell count and differential	X		X		X		X		X	X	X	X	X
Platelet count	X		X		X		X		X	X	X	X	X
Clinical chemistry													
Aspartate Aminotransferase (AST, serum glutamic oxaloacetic transaminase (SGOT))	X		X		X		X		X	X	X	X	X
Alanine Aminotransferase (ALT, serum glutamic pyruvic transaminase (SGPT))	X		X		X		X		X	X	X	X	X
Alkaline Phosphatase	X		X		X		X		X	X	X	X	X

Table 6 Safety laboratory variables Period A, B, C

Visit number	1	2	3	4	5	6	7	8	9	10	11	12	13
Study week	-21 - 17 days	-2 w	0 w	3 w	6 w	9 w	12 w	15 w	18 w	24 w	30 w	39 w	52 w
CK	X		X		X		X		X	X	X	X	X
Total Bilirubin	X		X		X		X		X	X	X	X	X
Blood Urea Nitrogen (BUN)	X		X		X		X		X	X	X	X	X
Electrolytes: - Sodium - Potassium - Chloride	X		X		X		X		X	X	X	X	X
Total protein	X		X		X		X		X	X	X	X	X
Albumin	X		X		X		X		X	X	X	X	X
TSH ^a	X												
Serum Creatinine (SCr), calculated Creatinine Clearance ^b	X		X		X		X		X	X	X	X	X
FSH ^c	X												
Hepatitis Screen Panel ^d	X												
Urinalyses													
РН	X		X				X			X		X	X
Protein ^e	X		X				X			X		X	X
Glucose	X		X				X			X		X	X

Table 6 Safety laboratory variables Period A, B, C

Visit number	1	2	3	4	5	6	7	8	9	10	11	12	13
Study week	-21 - 17 days	-2 w	0 w	3 w	6 w	9 w	12 w	15 w	18 w	24 w	30 w	39 w	52 w
Leukocyte esterase ^e	X		X				X			X		X	X
Blood by dipstick ^e	X		X				X			X		X	X
Pregnancy test ^f	X		X	X	X	X	X	X	X	X	X	X	X
Albumin:creatinine ratio	X		X				X			X		X	X
Additional laboratory tests													
If elevated Serum Creatinine (SCr): - SCr	X		X				X			X		X	X

Table 6 Safety laboratory variables Period A, B, C

Visit number	1	2	3	4	5	6	7	8	9	10	11	12	13
Study week	-21 - 17 days	-2 w	0 w	3 w	6 w	9 w	12 w	15 w	18 w	24 w	30 w	39 w	52 w
If lymphocytopenia ^g - Absolute lymphocyte count	X		X		X		X		X	X	X	X	X
- Complete Blood Count (CBC) with differential	X		X		X		X		X	X	X	X	X
- Lymphocyte subsets including:	X		X		X		X		X	X	X	X	X
- Cluster designation: cell surface marker expressed by lymphocytes (CD4) + counts													
- Cluster designation: cell surface marker expressed by lymphocytes (CD8) + counts													

Table 6 Safety laboratory variables Period A, B, C

Visit number	1	2	3	4	5	6	7	8	9	10	11	12	13
Study week	-21 - 17 days	-2 w	0 w	3 w	6 w	9 w	12 w	15 w	18 w	24 w	30 w	39 w	52 w
If thrombocytopenia ^h													
- Thrombocyte count	X		X		X		X		X	X	X	X	X
- CBC with differential	X		X		X		X		X	X	X	X	X
- Peripheral blood smear	X		X		X		X		X	X	X	X	X
- Antiplatelet antibodies	X		X		X		X		X	X	X	X	X
- Test for faecal occult blood	X		X		X		X		X	X	X	X	X

^a If abnormal, reflex to free T4

b Creatinine clearance will be estimated by the method of Cockcroft and Gault

For women on hormone replacement therapy

Includes HBsAg and anti-HCV (if positive, reflex to immunoassay for hepatitis C RNA (RIBA HCV)).

Microscopy if dipstick positive for blood, leukocyte esterase or protein

Urine hCG pregnancy test for WOCBP (hCG minimum sensitivity of 25 IU/L) (dipstick analysed at the study centre)

See Appendix D

h See Appendix E

Table 7 Safety laboratory variables Period D

Visit number	14	15	16	17
Study week	65 w	78 w	91 w	104 w
Haematology				
Haemoglobin	X	X	X	X
Haematocrit	X	X	X	X
Red blood cell count	X	X	X	X
White blood cell count and differential	X	X	X	X
Platelet count	X	X	X	X
Clinical chemistry				
AST	X	X	X	X
ALT	X	X	X	X
Alkaline Phosphatase	X	X	X	X
CK	X	X	X	X
Total Bilirubin	X	X	X	X
BUN	X	X	X	X
Electrolytes: - Sodium	X	X	X	X
- Potassium - Chloride				
Total protein	X	X	X	X
Albumin	X	X	X	X

Table 7 Safety laboratory variables Period D

Visit number	14	15	16	17
Study week	65 w	78 w	91 w	104 w
SCr, calculated Creatinine Clearance ^a	X	X	X	X
Urinalyses				
РН	X	X	X	X
Protein ^b	X	X	X	X
Glucose	X	X	X	X
Leukocyte esterase ^b	X	X	X	X
Blood by dipstick ^b	X	X	X	X
Albumin:creatinine ratio	X	X	X	X
Pregnancy test ^c	X	X	X	X
Additional laboratory tests				
If elevated SCr:				
- SCr	X	X	X	X
If lymphocytopenia ^d				
- Absolute lymphocyte count	X	X	X	X
- CBC with differential	X	X	X	X
- Lymphocyte subsets including:	X	X	X	X
- CD4 + counts				
- CD8 + counts				

Table 7 Safety laboratory variables Period D

Visit number	14	15	16	17
Study week	65 w	78 w	91 w	104 w
If thrombocytopenia ^e				
- Thrombocyte count	X	X	X	X
- CBC with differential	X	X	X	X
- Peripheral blood smear	X	X	X	X
- Antiplatelet antibodies	X	X	X	X
- Test for faecal occult blood	X	X	X	X

^a Creatinine clearance will be estimated by the method of Cockcroft and Gault

Microscopy if dipstick positive for blood, leukocyte esterase or protein

^c Urine hCG pregnancy test for WOCBP (hCG minimum sensitivity of 25 IU/L) (dipstick analysed at the study centre)

d See Appendix D

e See Appendix E

4.7.2.2 Derivation or calculation of outcome variables

Creatinine clearance will be estimated by the method of Cockcroft and Gault.

4.7.3 Vital signs, ECG and physical examination

4.7.3.1 Methods of assessment

Pulse and blood pressure

One pulse measurement will be taken after the patient has been sitting and resting for at least 5 minutes and before blood samples are taken. The pulse measurement will be followed by three blood pressure measurements, using a standardized cuff adapted to the size of the patient's arm.

ECG

A 12-lead ECG will be taken (supine position, standard ECG with a paper speed of 50 mm/second covering at least 6 sequential beats) after the patient has been lying down resting for at least 5 minutes. The ECG will be evaluated by the investigator and entered as 'Normal' or 'Abnormal' in the eCRF.

Weight and height

The patient's weight will be recorded in kilogram (kg), to one decimal place, on a fasting stomach with light clothing and no shoes. The patient's height will be recorded in centimetres, with no shoes.

Waist circumference

The waist should be measured in the morning before breakfast in the standing position at the natural waist (smallest waist circumference). If there is no natural waist, the measurement should be made at the level of the umbilicus.

Physical examinations

The physical examination includes the following: General appearance including skin inspection, lymph nodes, thyroid, musculoskeletal/extremities, cardiovascular, lungs, abdomen, and reflexes. Baseline data is collected at Visit 3, and new findings at the following physical examinations are recorded as change from baseline.

4.7.3.2 Derivation or calculation of outcome variables

The mean blood pressure measurements (diastolic and systolic blood pressure) will be computed by AstraZeneca for each patient at each visit. Body Mass Index (BMI) will be computed using the formula weight/height².

4.7.4 Other safety measurements and variables

4.7.4.1 Methods of assessment

Self-monitoring of plasma glucose should be done in order to reduce risk of prolonged periods of undetected hyperglycaemia or to confirm hypoglycaemia. Patients will be asked to do self-

monitoring of plasma glucose using glucometers provided by AstraZeneca. The patients will receive instruction on the use of the glucometer, according to the manufacturer's instruction.

Fasting plasma glucose concentrations

FPG should be self-monitored at least every second day during the lead-in and titration period, and at least once a week during the remaining treatment and extension periods. The patient diary will be collected from Visit 3 and kept in the investigator study file and a new diary for the next period will be handed over to the patient, if needed.

If self-monitored FPG is above 15 mmol/L, 270 mg/dL, the patient is highly recommended to repeat the self-monitoring of FPG within 2 days. If this second FPG is above 15 mmol/L, 270 mg, the patient should contact the study centre and, if appropriate, be scheduled for a FPG measurement at the centre (analysed by the central laboratory).

Hypoglycaemic events

The patient will be asked to always self-monitor plasma glucose and symptoms suggestive of hypoglycaemia and to register if a finger stick value was obtained and the glucose value in the supplied patient diary.

A hypoglycaemic event can be either

- An episode with symptoms and confirmed low glucose.
- An episode with low glucose.
- An episode with symptoms when glucose not was measured.

For the evaluation of hypoglycaemic events special attention will be given to hypoglycaemia as defined in accordance with the Committee for Proprietary Medicinal Products' guidance on clinical investigation of medicinal products in the treatment of diabetes mellitus (CPMP 2002), as described below.

Major hypoglycaemic events, defined as symptomatic events requiring external assistance due to severe impairment in consciousness or behaviour, with blood glucose level <3.0 mmol/L, <54 mg/dL, and prompt recovery after glucose or glucagon administration.

Minor hypoglycaemic event, defined as either a symptomatic event with blood glucose level <3.0 mmol/L, <54 mg/dL, and no need for external assistance, or an asymptomatic blood glucose measurement <3.0 mmol/L, <54 mg/dL.

Events suggestive for hypoglycaemia, with symptoms that the patient experiences as hypoglycaemia and no confirmative measurement.

Plasma glucose values, not blood glucose values, will be obtained from the central laboratory and when using the site based glucose analyser and glucometers provided by AstraZeneca.

Therefore, the corresponding plasma glucose values will be used to define hypoglycaemia, ie, plasma glucose <3.5 mmol/L, <63 mg/dL.

Data to be collected for each hypoglycaemic event:

- Date of start and stop and time of the day for start
- If symptoms are present or not and which symptoms
- If fingerstick value obtained and the plasma glucose value
- Intervention needed for recovery, max intensity, action taken, causality and possible contributing factors

The patient diary will be reviewed and data regarding hypoglycaemic events transcribed into the eCRFs at each clinical visit. A new diary for the next period will be handed over to the patient if needed. If a major hypoglycaemic event occurs, or more than one minor since last visit, the patient should contact the investigator. For recording of hypoglycaemic events/symptoms suggestive of hypoglycaemic events as AEs, see Section 4.7.1.2.

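### The patient-contact instruction in 4.7.4.1 does not cover a single assisted hypoglycaemic episode with no glucose reading or without prompt recovery

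*Protocol*

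**What the plan says.** Protocol section 4.7.4.1 first counts three kinds of episode as hypoglycaemic events: symptoms with a confirmed low value, a low value alone, and "An episode with symptoms when glucose not was measured". It then sets out classes that it attributes to the 2002 CPMP guidance:

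- **Major:** a symptomatic event needing outside help because of severe impairment, "with blood glucose level <3.0 mmol/L, <54 mg/dL, and prompt recovery after glucose or glucagon administration".
- **Minor:** one of two kinds. Where there are symptoms, it is a "symptomatic event with blood glucose level <3.0 mmol/L, <54 mg/dL, and no need for external assistance". Where there are none, any reading under the same cut-off is enough.
- **Suggestive:** "Events suggestive for hypoglycaemia, with symptoms that the patient experiences as hypoglycaemia and no confirmative measurement".

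Because the meters and laboratory report plasma glucose, "the corresponding plasma glucose values will be used to define hypoglycaemia, ie, plasma glucose <3.5 mmol/L, <63 mg/dL". This changes the cut-off and leaves the other conditions as they are.

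The instruction to the patient is: "If a major hypoglycaemic event occurs, or more than one minor since last visit, the patient should contact the investigator". The scheduled route by which the site learns of events is the diary: "The patient diary will be reviewed and data regarding hypoglycaemic events transcribed into the eCRFs at each clinical visit".

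Discontinuation criterion 8 in section 3.3.5.1 uses the same two labels, major and recurring minor. Criterion 2 in the same list allows discontinuation for safety on judgement, without reference to any label.

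**The concern.** The contact instruction works through the labels, and the label *major* rests on more than clinical severity. It also needs a glucose value and a prompt response to treatment. A patient with severely impaired consciousness is the one least able to take a fingerstick, and a helper may reasonably treat first. On the text as written, that episode does not ask the patient to call, whereas two low readings without symptoms do.

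What is at stake is notification between visits. Down-titration, discontinuation on safety grounds and SAE reporting all begin once the site knows of the event. The contact sentence is the stated rule for making it known before the next visit.

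**Working it through.** The plan gives no figure on this point, so there is none to reproduce. The check has three parts: classify the events, test them against the contact rule and the endpoint, and read the visit gaps.

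**1. Classes.** The definitions of section 4.7.4.1, with plasma glucose <3.5 mmol/L as low, give:

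| Event | Glucose | Recovery | Class | Does one event ask for contact? |
|---|---|---|---|---|
| Assisted, severe impairment | low | prompt | major | yes |
| Assisted, severe impairment | low | not prompt | none | no |
| Assisted, severe impairment | not measured | either | suggestive | no |
| Symptoms, no assistance needed | low | either | minor | no; yes from the second |
| No symptoms | low | not applicable | minor | no; yes from the second |

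The second row fails *major* on recovery. It fails *minor* because assistance was needed, and *suggestive* because a confirming value exists. The third row is suggestive, since that class makes no exception for assisted events. Repeating either kind does not turn it into a minor event. An assisted episode with a measured value that was not low is not a hypoglycaemic event under 4.7.4.1 and lies outside this point.

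**2. Endpoint.** The key secondary variable in section 6.2 is the proportion of patients with at least one hypoglycaemic event. The second row counts as an episode with low glucose. The third counts as an episode with symptoms and no measurement. Both are already included.

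**3. Time to the next scheduled visit.** Nominal visit weeks from Table 3 are 0, 3, 6, 9, 12, 15, 18, 24, 30, 39, 52, 65, 78, 91 and 104.

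| Weeks | Gaps | Longest wait | Mean wait (gap/2) |
|---|---|---|---|
| 0–18 | 6 × 3 weeks | 3 weeks | 1.5 weeks |
| 18–30 | 2 × 6 weeks | 6 weeks | 3 weeks |
| 30–39 | 1 × 9 weeks | 9 weeks | 4.5 weeks |
| 39–104 | 5 × 13 weeks | 13 weeks | 6.5 weeks |

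The 13-week gaps cover 5 × 13 = 65 of 104 weeks, or 65/104 = 62.5%. The mean wait assumes that events fall evenly within a gap. All figures use nominal dates and assume no spontaneous call and no SAE report, so they describe the calendar and bound any delay from above.

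**The case against.** The other side has several good arguments, and most of them limit the weight of the point.

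- **The classes are presented as regulatory ones, and requiring a confirmed value is a common choice.** This stands for the reported classes. It does not oblige the protocol to use the same label to decide when a patient should telephone.
- **An unmeasured event should be uncommon.** Every patient has a glucometer and is asked always to self-monitor, and nothing says that the patient must take the reading, so a helper's value would count. This stands; the frequency cannot be derived from the protocol.
- **SAE reporting covers many of these events.** Section 4.7.1.2 sends hypoglycaemia that meets the SAE definition to that route, and Appendix B leans towards seriousness for events that may need intervention to prevent a serious outcome. This stands, especially for slow recovery, so the practical gap is mainly the unmeasured event. The one-day clock in section 4.7.1.4 still starts only when the investigator becomes aware.
- **The comparison with two symptom-free readings mixes a frequency trigger with a severity trigger.** That is fair. It illustrates the rule and is not evidence that the designers ranked the two patterns.

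A reader might also infer that criterion 8 is defective and should be widened. The protocol does not support that. Criterion 8, too, operates only once the investigator knows of the event, and by then criterion 2 applies whatever the class. Section 3.3.5.1 also lets patients be discontinued at any time. Adding unconfirmed events to a named discontinuation reason has its own cost: extra stops would plausibly fall more on glipizide, and the per-protocol set in section 6.3.3 requires completion of 52 weeks.

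**Conclusion.** The gap in the contact sentence is real and narrow. As written, an episode needing outside help for severe impairment does not ask for contact if no glucose was measured, or if glucose was low and recovery was not prompt. The unmeasured case is the one that matters in practice.

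Two further inferences should be resisted. The hypoglycaemia endpoint is not miscounted, because both kinds of event enter it, and no hypothesis is affected. Nor does the protocol show that safety action would be delayed by 13 weeks: that figure is the longest nominal visit gap, reached only if the patient stays silent and no SAE is reported. Many patients would call anyway, and patient-facing instructions not shown here may ask for more than section 4.7.4.1 does.

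Severity is minor: a cheap improvement to patient safety.

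**What to change.** Amend only the contact sentence in section 4.7.4.1. After the major-event trigger, insert: *or any hypoglycaemic or suspected hypoglycaemic event requiring external assistance (whether or not glucose was measured)*. Keep the trigger for more than one minor event. Keep the major, minor and suggestive classes for reporting, and leave criterion 8 unchanged. The insertion leaves out severe impairment on purpose, so that the patient need not judge it.

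The cost is one sentence, carried through the amendment process of section 7.4 and into any patient instructions that repeat it. No data item, endpoint or analysis is added, since the intervention needed for recovery is already collected for each event. The downside is a few additional contacts after unconfirmed assisted episodes, some of which will prove trivial.

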4.7.5 Independent Adjudication Committee

An Independent Adjudication Committee, blinded to the treatment of the patient, will classify cardiovascular adverse events, such as, but not limited to, death, myocardial infarction, and stroke reported in the study. A separate Adjudication Manual will define and describe the procedure for the handling, reporting and classification of these events.

4.8 Volume of blood sampling and handling of biological samples

The total volume^a of blood that will be drawn from each patient in this study is as follows:

Assessment		Total volume (mL)
Efficacy and safety	Clinical chemistry	200
	Haematology	74 (146)
Exploratory		30
Pharmacokinetic		(72)
Plasma concentration		(3)
OGTT		(210)
Genotyping		10
Total		314 (671)

Pharmacokinetic and OGTT samples will be carried out on patients in a selection of countries (50 patients). The blood volume stated within brackets for haematology may be applicable for patients in the algorithm for trombocytophenia and/or lymphocytophenia (depending on number of blood sample visits). One plasma

concentration sample taken if the patient experience any of the predefined AEs (see 4.7.1.3) or discontinue from the study due to an AE.

